5.2. Patient Compliance

5.2.1. Parenterally Administered Investigational Products

For avelumab, utomilumab, PF-04518600, PD 0360324, and CMP-001, the site will complete required dosage Preparation Record located in the Investigational Product Manual. The use of the Preparation Record is preferred but it does not preclude the use of an existing appropriate clinical site documentation system. The existing clinical site's documentation system should capture all pertinent /required information on the preparation and administration of the dose. This may be used in place of the Preparation Record after approval from the Pfizer monitor.

5.3. Investigational Product Supplies

5.3.1. Avelumab (MSB0010718C)

Avelumab (MSB0010718C) will be supplied for the study by Pfizer Global Clinical Supply, Worldwide Research and Development. Drug supplies will be shipped to the study sites with a Drug Shipment and Proof of Receipt form. This form will be completed, filed, and the shipment confirmed as directed on the bottom of the Drug Shipment and Proof of Receipt form. The Investigator shall take responsibility for and shall take all steps to maintain appropriate records and ensure appropriate supply, storage, handling, distribution, and usage of investigational products in accordance with the protocol and any applicable laws and regulations.

5.3.2. Other Immune Modulators

PF-05092566, PF-04518600, PD 0360324 and CMP-001 investigational products and CMP-001 diluent will be supplied for the study by Pfizer Global Clinical Supply, Worldwide Research and Development. See details above for avelumab ([Section 5.3.1](#)).

5.3.3. Formulation/Dosage Forms and Packaging

5.3.3.1. Avelumab (MSB0010718C)

Avelumab (MSB0010718C) is a sterile, clear, and colorless solution intended for IV administration. It is presented with a nominal volume of 10 mL at a concentration of 20 mg/mL in single-use glass vials closed with a rubber stopper and sealed with an aluminum polypropylene flip off seal. The vial is intended for single use only.

Avelumab will be shipped under refrigerated conditions (2°C to 8°C) that are monitored with temperature control monitoring devices.

5.3.3.2. Other Investigational Products

5.3.3.2.1. Utomilumab (Combinations A, D and F)

Utomilumab is a sterile, colorless solution intended for IV administration. It is presented at a concentration of 10 mg/mL with a nominal volume of 10 mL in glass vials closed with a rubber stopper and sealed with an aluminum overseal. The vial is intended for single use only.

Utomilumab will be shipped under refrigerated conditions (2°C to 8°C) that are monitored with temperature control monitoring devices.

5.3.3.2.2. PF-04518600 (Combinations B, D and F)

PF-04518600 10 mg/mL injection is presented as a sterile solution for IV administration. Each vial has a nominal volume of 10 mL, is sealed with a coated stopper and an overseal, and labeled according to local regulatory requirements. The vial is intended for single use only.

PF-04518600 will be shipped under refrigerated conditions (2°C to 8°C) that are monitored with temperature control monitoring devices.

5.3.3.2.3. PD 0360324 Combination C

PD 0360324 is provided 75 mg/vial as a powder for solution for injection for IV administration. The drug product is supplied in a clear glass vial with an appropriate stopper and an aluminum overseal. The formulation consists of the active drug substance containing the precedented excipients. The vial is intended for single use only.

PD 0360324 will be shipped under refrigerated conditions (2°C to 8°C) that are monitored with temperature monitoring devices.

5.3.3.2.4. CMP-001 Combination F

The CMP-001 drug product will be supplied at a concentration of 5 mg/mL. CMP-001 is a colorless to pale yellow/brown opalescent liquid. Each single-use vial contains an extractable volume of 1 mL (with an overfill of 0.1 mL). Please refer to the Pharmacy Manual for dose preparation. CMP-001 will be shipped under refrigerated conditions (2°C to 8°C) that will be monitored with temperature monitoring devices.

5.3.3.2.5. CMP-001 Diluent

The CMP-001 diluent product will also be supplied by Pfizer Inc. CMP-001 diluent is a colorless to pale yellow/brown opalescent liquid. Each single-use vial contains an extractable volume of 10 mL. Please refer to the dosage and administration (DAI) section of the Investigational Product (IP) manual for dose preparation. CMP-001 diluent will be shipped under refrigerated conditions (2°C to 8°C) that are monitored with temperature monitoring devices.

5.3.4. Preparation and Dispensing

Investigational products must not be used for any purpose other than the trial.

5.3.4.1. Parenterally Administered Investigational Products

For avelumab, utomilumab, PF-04518600, PD 0360324, and CMP-001, please see the dosage and administration instructions (DAI) section of the Investigational Product (IP) Manual for instructions on how to prepare the investigational products for administration. The IV investigational products should be prepared and dispensed by an appropriately qualified and

experienced member of the study staff (eg, physician, nurse, physician's assistant, practitioner, pharmacist, or medical assistant) as allowed by local, state, and institutional guidance.

Only qualified personnel who are familiar with procedures that minimize undue exposure to them and to the environment should undertake the preparation, handling, and safe disposal of hazardous agents.

Any unused portion of the solution should be discarded in biohazard waste disposal with final disposal by accepted local and national standards of incineration.

Any spills that occur should be cleaned up using the facility's standard cleanup procedures for biologic products.

Detailed information on infusion bags and medical devices to be used for the preparation of the dilutions and subsequent administration(s) for each investigational product will be provided in the DAI section of the IP Manual.

5.3.5. Administration

5.3.5.1. Parenterally Administered Investigational Products

Avelumab, utomilumab, PF-04518600, and PD 0360324 investigational products will be administered IV at the investigational site on an outpatient basis. After Cycle 1, IV investigational products may be administered up to 2 days before or after the scheduled treatment day of each cycle for administrative reasons. However, if the IV administration is given 2 days before or after the scheduled treatment day, and multiple IV investigational products are to be administered, all scheduled IV investigational products should be given on the same day. Patients will be observed in the clinic for at least 2 hours after the last infusion of investigational product. If, following the 4th infusion of avelumab, no infusion reaction is observed, the post-infusion observation period may be discontinued thereafter.

Avelumab (all combinations) will be administered at 10 mg/kg as a 1-hour IV infusion Q2W on Day 1 and Day 15 of each cycle. Note: for all patients except those in Cohort A9, avelumab administration will start on Cycle 1 Day 1. For patients randomized to Cohort A9, avelumab administration will begin on Cycle 2 Day 1.

Utomilumab (Combination A, Combination D and Combination F) will be administered as a 1-hour IV infusion Q4W on Day 1 of each cycle. Note: for all patients except those in Cohort A10, utomilumab administration will start on Cycle 1 Day 1. For patients randomized to Cohort A10, utomilumab administration will begin on Cycle 2 Day 1.

PF-04518600 (Combination B, Combination D and Combination F) will be administered as a 1-hour IV infusion, Q2W on Day 1 and Day 15 of each cycle.

PD 0360324 (Combination C) will be administered as a 30-minute IV infusion Q2W on Day 1 and Day 15 of each cycle.

Avelumab, utomilumab, and PF-04518600 are to be administered as a 1-hour IV infusions; PD 0360324 is to be administered as a 30-minute IV infusion. Sites should make every effort to target infusion timing to be as close to the duration specified for the investigational product as possible. However, the 1-hour infusion(s) administered over 50-80 minutes will be considered protocol compliant. The accepted window for a 30 min infusion is ± 10 minutes. The exact duration of infusion should be recorded in both source documents and CRFs. Dose reduction for toxicity management for any of the investigational products is not permitted, however next cycle administration may be omitted due to persisting toxicity as described in [Table 21](#) and [Section 5.3.7.2](#).

The dose amount required to prepare the dose for weight-based infusion solutions (ie, avelumab and PF-04518600) will be based on the patient's weight in kilograms (kg). All patients should be weighed within 3 days prior to dosing for every cycle. If the patient experienced either a weight loss or gain $>10\%$ compared to the weight used to calculate the prior dose, the amount of investigational product required for preparation and administration for the current cycle must be recalculated using this most recent weight obtained. If weight change is $\leq 10\%$ compared to the weight used to calculate the prior dose, dose recalculation is optional and the site should follow their standard practice.

CMP-001 will be administered initially as 2 weekly SC doses followed by IT dosing at weekly intervals for 5 additional doses. After the first 7 doses, CMP-001 will be administered IT every 2 weeks (Q2W) (all cohorts). From C2D1, if IT administration is not feasible then CMP-001 should be administered in the peritumoral region. If peritumoral administration is not feasible, then SC administration in an area of the draining lymph node where primary disease exists should be implemented. If any of the above is not feasible, then SC (either arm, thigh, or anterior abdominal wall) administration should be implemented. CMP-001 administration and requirements are summarized in Table 20.

Table 20. CMP-001 Administration and Requirements

Visit/Dose	CMP-001 Administration ^a		Premedications	Post injection Observation Period
C1D1 and C1D8	SC (either arm, thigh or anterior abdominal wall)	Weekly	Mandated	Required (4 hrs)
C1D15, C1D22, C2D1, C2D8	IT ^b	Weekly	Mandated	Required (4 hrs)
C2D15 onwards	IT ^b	Every 2 weeks	Recommended	Required (can be reduced up to 1 hr based on reactions to prior injections and clinical judgement).

C=cycle; D=day; hr=hour; IT=intratumoral; SC=subcutaneous.

a. CMP-001 will be administered initially as 2 weekly SC doses, followed by IT dosing at weekly intervals for 5 additional doses. After the first 7 doses, CMP-001 will be administered IT every 2 weeks (Q2W) (all cohorts).

b. From C2D1, if IT is not feasible then CMP-001 should be administered in peritumoral region. If peritumoral administration is not feasible, then SC administration in an area of the draining lymph node where primary disease exists should be implemented. If any of the above is not feasible, then SC (either arm, thigh or anterior abdominal wall) should be implemented.

Detailed instructions for CMP-001 administration, including tumor lesion selection and dose splitting, are provided in [Appendix 4](#) and in the Injection Manual.

5.3.5.2. Timing of Investigational Product Administration

For Combinations A, B, and C, the avelumab infusion is to be administered at least 30 minutes (+20-minute time window, if needed) after the end of the infusion of the other investigational product.

For Combination D, on days when three investigational products are to be administered, utomilumab will be administered first, followed at least 30 minutes (+20-minute time window, if needed) later by the PF-04518600 infusion (second), followed at least 30 minutes (+20-minute time window, if needed) later by the avelumab infusion (third). On days when only avelumab and PF-04518600 are administered, PF-04518600 will be administered first followed by the avelumab infusion at least 30 minutes (+20-minute time window, if needed) after the end of the PF-04518600 infusion.

For Combination F, on days when two investigational products are to be administered (CMP-001 and avelumab), avelumab will be administered first followed by CMP-001. On days when three investigational products are to be administered, either utomilumab (Cohort F2) or PF-04518600 (Cohort F3) will be administered first, followed by avelumab and then followed by CMP-001. A 30 to 50 minute window is recommended between administration of the individual drugs to conduct end of infusion/injection procedures (eg, sample collections) and accommodate any logistical arrangements (eg, drug preparation, moving patient from one location to another for treatment administration etc.). The drug administration visits can be spread over two consecutive days eg, avelumab alone or avelumab and utomilumab or avelumab and PF-04518600 to be administered on 1 day (eg, C1D1) and CMP-001 to be administered on the next day (eg, C1D2).

For Combination F, during the Phase 2 part of the study, the order of drug administration can be changed for individual patients to address any logistical issues to accommodate IT injections. Such changes should be discussed with the medical monitor of the study before implementation.

On days when PK samples are taken, samples will be taken relative to dosing as described in the [Schedule of Activity](#) tables.

Premedication for avelumab in Combinations A, B, C, D, and F:

Avelumab premedication: in order to mitigate infusion-related reactions, patients must be premedicated with an antihistamine and with paracetamol (acetaminophen) prior to the first four infusions of avelumab. Premedication should be administered for subsequent avelumab doses based upon clinical judgment and presence and severity of prior infusion reactions. In Combinations A, B, C, and D, when two or three investigational products are to be administered on the same day, premedication should be given prior to the first investigational

product administration. This may be modified based on local treatment standards and guidelines.

Premedication in Combination F:

To reduce the severity of symptoms associated with CMP-001 induced cytokines, prophylaxis is mandated prior to the initial two SC (C1D1 and C1D8) and four IT (C1D15, C1D22, C2D1, C2D8) doses.

The following premedication regimen is mandated in prevention of CMP-001 induced reactions unless clinically contraindicated:

- Fluids (ie, 1000 mL IV normal saline);
- NSAIDS (ie, 1000 mg acetaminophen and 50 mg indomethacin);
- Anti-emetics (ie, 8 mg Zofran orally [per os (PO)]).

It is also highly recommended to continue to administer additional fluids **immediately following** the CMP-001 injection, rather than waiting to initiate fluids when hypotension is detected.

If some of these premedications are administered prior to avelumab infusion, they may not need to be repeated before CMP-001 administration. If the drug administration visit is spread over two consecutive days, appropriate premedication should be administered on both days, according to the study drug being administered on each day. Premedication for subsequent CMP-001 doses (C2D15 onwards) is recommended and should be administered based upon clinical judgment and presence and severity of prior infusion reactions. The CMP-001 premedication requirements are summarized in [Table 20](#).

Stress Dose Steroids

Prophylaxis with stress dose steroids is recommended for patients who have experienced CMP-001-related Grade 3 CRS lasting ≤ 24 hours (ie, a minimum dose of corticosteroids of 25 mg prednisone or equivalent [eg, hydrocortisone, methylprednisolone, and dexamethasone]) for subsequent CMP-001 doses. The selection and dose of corticosteroid should be determined by the Investigator based on clinical parameters.

Patients with a history of adrenal insufficiency are at increased risk for moderate to severe AEs such as hypotension which may occur with 1 to 4 hours after injection. It is strongly recommended that these patients receive stress dose steroids (eg, 50 to 100 mg hydrocortisone administered orally [PO] every 8 hours [Q8]) prior to and for 24 to 48 hours following CMP-001 injection.

Post Administration Observation Period

Combinations A, B, C, D

Patients will be observed in the clinic for at least 2 hours after the last infusion of investigational product. If, following the fourth infusion of avelumab, no infusion reaction is observed, the post-infusion observation period may be discontinued thereafter.

Combination F

CMP-001 post-injection observation period: the observation period is mandated after the initial two SC (C1D1 and C1D8) and four IT (C1D15, C1D22, C2D1, and C2D8) doses. Patients must be observed for a period of at least 4 hours following each of the CMP-001 injections for signs and symptoms of reactions to the injection and other AEs. Vital signs including measurement of blood pressure (systolic and diastolic blood pressure [mmHg]), respiratory rate, heart rate (bpm), and body temperature (°C) are to be collected prior to CMP-001 injection, and at 30 (± 15) minute intervals during the post-infusion observation period. Starting on C2D15, the observation period can be reduced to 1 hour based on the investigators assessment of AE profile associated with prior injections.

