3.3. Dose-Limiting Toxicity Definition

Severity of AEs will be graded according to CTCAE v.4.03. For the purpose of the Phase 1b lead-in, any of the following AEs occurring during the DLT observation period (the first 2 cycles of treatment [8 weeks] for combinations A to D, and the first treatment cycle [4 weeks] for combination F) which are attributable to one or more of the investigational products in the combination will be classified as DLTs:

Hematologic:

- Grade 4 neutropenia (absolute neutrophil count [ANC] <500/mm³ or <0.5 x 10⁹/L) lasting >7 days;
- Febrile neutropenia, defined as ANC <1000/mm³ with a single temperature of >38.3 degrees C (>101 degrees F) or a sustained temperature of ≥38 degrees C (100.4 degrees F) for more than 1 hour;
- Neutropenic infection (ANC <1,000/mm³ or <1.0 x 10⁹/L, and Grade >3 infection);
- Grade ≥3 thrombocytopenia (platelet count <50,000 - 25,000/mm³ or <50.0 – 25.0 x 10⁹/L) with bleeding;
- Grade 4 thrombocytopenia (platelet count <25,000/mm³ or <25.0 x 10⁹/L);
- Grade 4 anemia.

Non-Hematologic (Non-Laboratory):

- Any Grade ≥3 toxicity, except for any of the following:
 - Transient (≤24 hours) Grade 3 fatigue, local reactions, or headache that resolves to Grade ≤1;

- Grade 3-4 nausea and vomiting controlled by optimal medical therapy within 72 hours;
- Grade 3 hypertension controlled by medical therapy;
- Grade 3 diarrhea that improves to Grade ≤ 2 within 72 hrs after medical management has been initiated;
- Grade 3 skin toxicity that resolves to Grade ≤ 1 in less than 7 days after medical management (eg, immunosuppressant treatment) has been initiated;
- Any Grade ≥ 3 amylase or lipase abnormality that is not associated with symptoms or clinical manifestations of pancreatitis;
- Grade 3 endocrinopathies controlled with medical therapy;
- Tumors flare phenomenon defined as local pain, irritation, or rash localized at sites of known or suspected tumor.
- Grade 4 CRS or Grade 3 CRS lasting >24 hours despite optimal treatment.

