5.3.7.2. Study Treatment Modifications for Investigational Products Drug-Related Toxicity

Recommended treatment modifications for the investigational product attributable to drug-related toxicity are shown in Table 21.

Table 21. Avelumab, Utomilumab, PF-04518600, PD 0360324, and CMP-001 Treatment Modifications for Drug-Related Toxicity

Toxicity	NCI CTCAE Severity Grade	Treatment Modification
Drug-related adverse reactions (excluding infusion-related reaction/hypersensitivity and immune-related AEs)	Grade 1	
Continue per schedule.
	Grade 2	
Continue per schedule.Consider withholding treatment for intolerable adverse reaction based on medical judgment.
	Grade 3	
Withhold until recovery to Grade 1 or better.If toxicity does not resolve to Grade 1 or better within 12 weeks of last administration or if based on medical judgment the event is considered critical, consider permanent discontinuation after consultation with the sponsor.Upon the second occurrence of the same Grade 3 toxicity that does not resolve to Grade ≤1 by the next administration, treatment must be permanently discontinued. 
Exceptions are: Laboratory values out of normal range that do not have any clinical correlation.

	Grade 4	
Permanent discontinuation. 
Exceptions are: Laboratory values out of normal range that do not have any clinical correlation.

Infusion-related Reaction	Grade 1-4	
See Section 5.3.7.3.1 and Table 22.
Hypersensitivity reactions	Grade 3-4	
See Section 5.3.7.3.2.
Immune-related AE (irAE)	Grade 1-4	
See Section 5.3.7.3.4 and Table 25.

5.3.7.3. Special Precautions for Avelumab, Utomilumab, PF-04518600, PD 0360324, and CMP-001 Administration

As with all monoclonal antibody therapies, there is a risk of allergic reactions including anaphylactic shock. Investigational products (biologics) should be administered in a setting that allows for immediate access to an intensive care unit or equivalent environment and administration of therapy for anaphylaxis, such as the ability to implement immediate resuscitation measures. Steroids (dexamethasone 10 mg), epinephrine (1:1,000 dilution), allergy medications (IV antihistamines), bronchodilators, or equivalents, and oxygen should be available for immediate access.

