Hypopituitarism/Hypophysitis (secondary endocrinopathies)	
If secondary thyroid and/or adrenal insufficiency is confirmed (eg, subnormal serum thyroxine with inappropriately low thyroid-stimulating hormone and/or low serum cortisol with inappropriately low adrenocorticotrophic hormone):
 
 Refer to endocrinologist for dynamic testing as indicated and measurement of other hormones (FSH, LH, GH/IGF-1, PRL, testosterone in men, estrogens in women). Hormone replacement/ suppressive therapy as appropriate. Perform pituitary MRI and visual field examination as indicated. 
If hypophysitis confirmed:
 
 Continue investigational product if mild or moderate symptoms with normal MRI. Repeat the MRI in 1 month. Withhold investigational product if severe symptoms or life-threatening symptoms of hypophysitis and/or abnormal MRI. Consider hospitalization. Initiate high-dose corticosteroids (1 to 2 mg/kg/day methylprednisolone IV or equivalent) followed by corticosteroids taper during at least 1 month. Add prophylactic antibiotics for opportunistic infections. 	
Resume investigational product once symptoms and hormone tests improve (with or without hormone replacement).
 
In addition, for hypophysitis with abnormal MRI, resume investigational product only once shrinkage of the pituitary gland on MRI scan is documented.
 
Continue hormone replacement/ suppression therapy as appropriate.

Table 25. Management of Immune-Related Adverse Events

Other irAEs (not described above)		
Grade of other irAEs (NCI-CTCAE v4)	Initial Management	Follow-up Management
Grade 2 or Grade 3 clinical signs or symptoms suggestive of a potential irAE	Withhold investigational product therapy pending clinical investigation.	If irAE is ruled out, manage as appropriate according to the diagnosis and consider resuming investigational product therapy. If irAE is confirmed, treated as Grade 2 or 3 irAE.
Grade 2 irAE or first occurrence of Grade 3 irAE	Withhold investigational product therapy. 1.0 to 2.0 mg/kg/day prednisone or equivalent. Add prophylactic antibiotics for opportunistic infections. Specialty consult as appropriate.	If improves to Grade ≤ 1 : Taper steroids over at least 1 month and resume investigational product therapy following steroids taper.

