- Prophylactic use: prophylactic use, eg, for the prevention of acute infusion-related reactions, constitutes concomitant use and is prohibited except stress steroids to prevent severe CRS reactions in patients enrolled into Combination F as specified in [Section 5.3.5.2](#).
- Intranasal, inhaled, topical steroids, or local steroid injections (eg, intra-articular injection) are permitted.
- There are no prohibited therapies during the Post-Treatment Follow-up Phase.

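### Table 21 does not contain the stop for Grade 3 CRS lasting over 24 hours that the 24-hour limit on steroid prophylaxis presupposes, so as written CMP-001 may be resumed after a DLT-level reaction

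*Protocol*

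**What the plan says.** Five places in the Protocol bear on a Combination F patient who has had CRS.

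- **Section 3.3** includes in the DLT definition: "Grade 4 CRS or Grade 3 CRS lasting >24 hours despite optimal treatment".
- **Section 5.3.5.2** on later CMP-001 doses: "Prophylaxis with stress dose steroids is recommended for patients who have experienced CMP-001-related Grade 3 CRS lasting" 24 hours or less. The only other group for whom it advises stress-dose steroids is patients with a history of adrenal insufficiency.
- **Section 5.6.4** says that prophylactic steroid use "constitutes concomitant use and is prohibited except stress steroids to prevent severe CRS reactions in patients enrolled into Combination F as specified in" Section 5.3.5.2.
- **Section 5.3.7.2, Table 21**, whose title ends "and CMP-001 Treatment Modifications for Drug-Related Toxicity", sends infusion-related reactions, hypersensitivity and immune-related events to their own sections. All other drug-related reactions fall in a general row. For Grade 3 the instruction is: "Withhold until recovery to Grade 1 or better". Discontinuation is to be considered if recovery takes more than 12 weeks or the event is judged critical. The one mandatory Grade 3 stop begins "Upon the second occurrence of the same Grade 3 toxicity that does not resolve to Grade" 1 or lower by the next administration. Grade 4 is a permanent stop.
- **Section 5.3.7.3.3** covers symptoms of cytokine release. It has a treatment algorithm (Figure 22, not shown) and a separate CRS grading scale (Table 23).

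**The concern.** A steroid recommendation that stops at 24 hours implies that nobody with longer Grade 3 CRS receives another CMP-001 dose. The dose-modification table should then say so, and it does not. It makes no distinction by duration and does not mention CRS.

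What is at stake is patient safety and consistent exposure. One site following Table 21 could re-challenge a patient after a prolonged severe reaction. Another, reading the 24-hour limit as an implied stop, could discontinue CMP-001 for the same event.

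**Working it through.** The Protocol gives no figure to reproduce here. The check is to set the rules side by side and follow one patient through them.

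**1. Which rule governs CRS.** Table 21 does not exclude CRS from its general row, so that row applies. The alternatives do not change the result:
- If CRS were handled as an immune-related event, the Table 25 entry "Grade 2 irAE or first occurrence of Grade 3 irAE" also withholds treatment and then resumes it.
- Table 22 is written for IV infusions, whereas CMP-001 is given subcutaneously or intratumorally. It also stops treatment for every Grade 3 reaction, which would leave no later dose for Section 5.3.5.2 to cover.

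**2. What the readable text yields.**

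| Event | Table 21 | Post-CRS steroid recommendation, Section 5.3.5.2 |
|---|---|---|
| Grade 3 CRS, 24 h or less | Withhold, then may resume | Yes |
| Grade 3 CRS, over 24 h | Withhold, then may resume | No, unless adrenal insufficiency |
| Grade 4 CRS | Permanent stop | Not needed |

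The middle row is the gap. When such an event persists despite optimal treatment, it is DLT-level under Section 3.3.

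**3. Whether the mandatory Grade 3 stop closes the gap.** It needs a second occurrence that is still unresolved at the next dose. In the weekly phase the interval is 7 × 24 = 168 hours. A Grade 3 CRS lasting more than 24 but less than 168 hours does not trigger it, however often it recurs.

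**4. Doses at stake.** The schedule is two weekly subcutaneous doses (C1D1, C1D8), then "IT dosing at weekly intervals for 5 additional doses" (C1D15, C1D22, C2D1, C2D8, C2D15). Section 1.2.5.3 says that reactions typically follow the third dose, which here is C1D15. After it, 5 − 1 = 4 weekly doses remain, and dosing every 2 weeks follows.

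**5. Protection that remains on re-dosing.** Section 5.3.5.2 mandates fluids, NSAIDs and anti-emetics, unless contraindicated, through C2D8. That covers three of the four remaining weekly doses; at C2D15 they are recommended. Section 5.6.4 permits steroids to treat CRS. What is missing is a recommendation for steroid prophylaxis, and more importantly the stop.

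**6. Frequency.** Section 1.2.5.3 reports related serious CRS in 2 of 113 melanoma patients (1.8%) given CMP-001 with pembrolizumab. Neither grade nor duration is given, so the rate of Grade 3 CRS over 24 hours cannot be derived from it.

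**The case against.** The strongest reply is that the stop rule may exist where it cannot be seen. Section 5.3.7.3 directs CRS management to Section 5.3.7.3.3, whose core is Figure 22, and a missing figure is not a gap in the plan. A CRS-specific stop there could be read as refining Table 21, whose entries are described as recommendations. This stands in part: absence from the whole Protocol cannot be shown. But Table 21 points elsewhere for three other reaction types and not for CRS, so its general row would still tell a site that dosing may resume.

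A reader might infer that the plan deliberately gives the worse reaction less protection. The documents do not support that. The summary of changes for Amendment 9 ties the 24-hour limit to a requirement to discontinue after longer Grade 3 CRS and after Grade 4 or higher. It is cited here for intent only. These patients get no prophylaxis because they are meant to get no further treatment.

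A reader might also infer that steroid prophylaxis is flatly forbidden to these patients. That goes too far. Section 5.3.5.2 recommends for one group without expressly excluding others, and it is arguable whether the cross-reference in Section 5.6.4 limits the patients or only the regimen. The safe statement is that they fall outside the recommendation.

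Finally, the investigator may always stop CMP-001 for an event judged critical or for unacceptable toxicity (Section 6.4). True, but that permits a stop and does not require one.

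**Conclusion.** The point holds as an inconsistency between Section 5.3.5.2 and Table 21. The first assumes that Grade 3 CRS over 24 hours ends CMP-001, while the second lets it resume. The result as written is possible re-dosing after a DLT-level event, with up to four weekly doses still to come if the reaction follows the first intratumoral dose.

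This rests on three assumptions: that CRS falls in Table 21's general row, that the event meets the full Section 3.3 wording including persistence despite optimal treatment, and that Figure 22 does not in practice override the table. The grading scale is also unsettled. Section 3.3 and Table 21 use CTCAE, while Section 5.3.7.3.3 prints its own CRS scale.

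DLT counting, the cohort expansion rule and the sample size are untouched. The number of patients affected cannot be estimated from the documents. It should be fixed because each case could be serious and the correction is small.

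**What to change.** Add a CRS row to Table 21, with a pointer to Section 5.3.7.3.3, stating:

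- Grade 3 CRS of 24 hours or less: withhold, then resume after recovery with stress-dose steroids as in Section 5.3.5.2.
- Grade 3 CRS over 24 hours, and Grade 4 CRS: permanently discontinue CMP-001.
- Which grading scale applies, CTCAE v4.03 or Table 23.
- Whether avelumab and utomilumab or PF-04518600 may continue once CMP-001 stops.

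Check that Figure 22 agrees. Do not close the gap by extending steroid prophylaxis to re-dosing after Grade 3 CRS over 24 hours; that would endorse the re-challenge that the 24-hour limit appears meant to rule out.

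The cost is one table row and a cross-reference in Section 5.3.5.2. The downside is that a few patients who recover from prolonged CRS lose later CMP-001 doses.
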